6. SAFETY

All safety analyses will be based on the safety analysis set based on actual treatment received, unless otherwise specified.

For all continuous safety variables, descriptive statistics will include the N, mean, standard deviation, median, minimum, and maximum. Categorical variables will be summarized using frequency counts and percentages.

6.1. Adverse Events

All adverse events whether serious or non-serious, will be reported from the time a signed and dated informed consent form (ICF) is obtained until 30 days after the last dose of study treatment, until the subject withdraws consent for study participation, or until the subject starts subsequent antimyeloma therapy, whichever occurs first. Adverse Events will be recorded in standard medical terminology and graded according to the National Cancer Institute Common Terminology Criteria for Adverse Events (NCI-CTCAE), Version 5.0. The verbatim terms used in the eCRF by investigators to identify AEs will be coded using the latest Medical Dictionary for Regulatory Activities (MedDRA) coding dictionary.

Unless otherwise specified, at each level (e.g., system organ class and/or preferred term) of subject summarization in reporting the incidence of the AE, a subject is counted once if one or more events were recorded.

All summaries of AEs will be based on treatment-emergent adverse events (TEAEs). TEAEs are defined as any AE that occurs after start of the first study treatment through 30 days after the last study treatment, or the day prior to start of subsequent antimyeloma therapy, whichever is earlier; or any AE that is considered drug-related (very likely, probably, or possibly related) regardless of the start date of the event; or any AE that is present at baseline but worsens in toxicity grade during the TEAE reporting period, or after the TEAE reporting but is considered drug-related by the investigator. If the event occurs on the day of the first study treatment and either event time or time of study drug are missing, then the event will be assumed to be treatment-emergent. If the event date is recorded as partial or completely missing, then the event will be considered as treatment-emergent unless it is known to be prior to the first study treatment based on partial onset date or resolution date.

The following AE summaries will be presented by treatment group.

- An overview of TEAEs, including the number and percentage of subjects with
 - TEAEs
 - treatment-emergent SAEs
 - TEAEs related to study treatment
 - TEAEs leading to discontinuation of study treatment which includes those subjects indicated as having discontinued treatment due to an AE on the End of Treatment Disposition CRF page
 - TEAEs leading to discontinuation of any study treatment with action taken of drug withdrawn on AE CRF page
 - TEAE by maximum toxicity grade of 1 to 5
 - deaths due to TEAE
- TEAEs by SOC and PT, and by maximum toxicity grade of 1 to 5
- Most common (>10% in either DR or D) TEAEs by SOC and PT
- TEAEs related to study treatment by SOC and PT

- TEAEs related to study treatment with toxicity grade 3 or 4 by SOC and PT
- TEAEs with toxicity grade 3 or 4 by SOC and PT
- Most common (>5% in either DR or D) TEAEs with toxicity grade 3 or 4 by SOC and PT
- TEAEs with toxicity grade 3 or 4 by SOC, PT and by treatment cycle of first onset
- TEAEs leading to dose modifications or drug interruptions of any study treatment(s) by SOC and PT where dose modifications refer to action taken of the AEs with dose reduced, dose increased, or dose delayed according to AE CRF page
- TEAEs leading to dose modifications or drug interruptions of lenalidomide by SOC and PT
- TEAEs leading to dose modifications or drug interruptions of daratumumab by SOC and PT
- Treatment-emergent SAEs by SOC and PT
- Treatment-emergent SAEs related to study treatment by SOC and PT
- Treatment-emergent SAEs by SOC, PT, and toxicity grade
- Most common (>2% in either DR or D) Treatment-emergent SAEs by SOC, and PT
- Treatment-emergent SAEs by SOC, PT and by treatment cycle of first onset (Cycles 1-2, Cycles 3-6. Cycles 7+)
- TEAEs leading to discontinuation of any study treatment by SOC, and PT. The AEs leading to discontinuation of any study treatment are based on AEs recorded in the AE CRF page with an action taken of drug withdrawal for any study treatment.
- TEAEs leading to discontinuation of study treatments per treatment disposition by SOC, PT, and toxicity grade 3/4. This summary includes TEAEs leading to discontinuation of study treatment for those subjects indicated as having discontinued study treatment due to an adverse event on the end of treatment CRF page.

6.2. Deaths

6.2.1. Death Due to TEAEs

TEAEs with outcome of death will be summarized by SOC and PT and a listing is to be provided. TEAEs with outcome of death due to COVID-19 will also be summarized by SOC and PT.

6.2.2. All Deaths

A summary of all death and cause of death will be tabulated overall and by treatment group. Specifically, the number of subjects who died during the study will be summarized for the safety analysis set. The primary cause of death collected on the death information CRF page will be reported. If the primary cause of death is an AE, the number of subjects who have a related AE and unrelated AE will be further summarized. The similar summaries will be presented for subjects who died within 30 days of last study treatment dose and within 60 days of first study treatment dose, respectively.

6.3. Adverse Events of Clinical Interest

6.3.1. Injection-Related Reactions (IRR) and Injection Site Reaction

Subjects with any treatment-emergent IRR and injection site reaction associated with daratumumab administration will be summarized by MedDRA SOC and PT. The summaries will be presented for all grades, Grade 3 or 4, Grade 5, and SAEs.

The number and percentage of subjects with IRRs will be summarized by time of injections (first injection, second injection or subsequent injections) and by MedDRA SOC and PT.

A listing of subjects with treatment-emergent IRR and injection site reaction associated with daratumumab administration will be provided.

6.3.2. Infections and infestations

Infections and infestations refer to adverse events with SOC of infections and infestations. A summary of number of subjects with 1 or more treatment-emergent infections and infestations will be summarized by MedDRA PTs for all grades, Grade 3 or 4, Grade 5, and SAEs. Additional summary analysis will be performed by onset time (i.e., ≤ 6 months vs. $6 - \leq 12$ months vs. >12 months) based on the first onset of the infections and infestations.

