Daratumumab (JNJ-54767414) is a human immunoglobulin G1 kappa monoclonal antibody that binds with high affinity to a unique epitope on CD38. The addition of daratumumab to bortezomib and dexamethasone or to lenalidomide and dexamethasone in the CASTOR and POLLUX studies, respectively, tripled the minimal residual disease (MRD) negative rate in patients with relapsed multiple myeloma, and patients who attained MRD negativity had significantly longer progression-free survival (PFS) than patients who remained positive. Similarly, in newly diagnosed myeloma patients, addition of daratumumab to standard of care regimens such as bortezomib plus melphalan and prednisone, bortezomib plus thalidomide and dexamethasone, as well as lenalidomide and dexamethasone, improved the MRD negativity rate and PFS significantly, as observed in the ALCYONE, CASSIOPEIA, and MAIA studies, respectively. Maintenance therapy with lenalidomide is the standard of care following frontline autologous stem cell transplant (ASCT) for multiple myeloma. Attainment of MRD negativity following ASCT and maintenance therapy has been shown to improve long-term outcomes. However, lenalidomide alone may not be sufficient to convert MRD positive patients post-transplant to MRD negativity. Therefore, to improve the likelihood of converting patients to MRD negativity, addition of subcutaneous (SC) daratumumab to lenalidomide maintenance treatment will be evaluated in Study MMY3021. We expect that the benefits of addition of SC daratumumab to lenalidomide, as maintenance treatment, will outweigh the risks, even among patients who may achieve a complete response (CR) or better after transplant. Prolonged administration of daratumumab in conjunction with lenalidomide does not result in an increased total risk of adverse events (AEs). In the MAIA study of IV daratumumab and Rd versus Rd alone in newly diagnosed patients with myeloma, the incidence of serious treatment-emergent (TE) AEs was similar in both treatment groups (62.9% in the DRd group and 62.7% in the Rd group). Of the most frequently reported (>10%) Grade 3 or 4 adverse events, higher rates of neutropenia (DRd: 50.0%; Rd: 35.3%), lymphopenia (DRd: 15.1%; Rd: 10.7%), leukopenia (DRd: 11.0%; Rd: 4.9%), and pneumonia (DRd: 13.7%; Rd: 7.9%) were observed in the DRd group, while Grade 3 or 4 anemia occurred more frequently in the Rd group (DRd: 11.8%; Rd: 19.7%). Although Grade 4 TEAEs were reported in a higher percentage of patients in the DRd group compared with the Rd group, fewer patients in the DRd group (7.1%) discontinued study treatment due to a TEAE compared with the Rd group (15.9%); however, the percentage of patients discontinuing lenalidomide was similar in both arms.

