1.2. Trial Design

This is a Phase 3, randomized, open-label, active-controlled, multicenter study to be conducted at sites in the United States (US) and Canada to primarily evaluate the conversion rate to MRD negativity following 12 months of maintenance treatment with SC daratumumab in combination with lenalidomide relative to treatment with lenalidomide alone in patients with newly diagnosed multiple myeloma who have received at least 4 cycles of induction with or without consolidation, have undergone HDT and ASCT within 12 months of the start of induction, are within 6 months of the ASCT date at the time of randomization, have very good partial response or better at the time of randomization, are MRD positive at the time of screening, and are anti-CD38 treatment naïve.

The study includes a Screening Period; a Maintenance Phase; an End of Treatment (EOT) Visit; and a Follow-up Phase as described below.

- Screening Period: Screening is to be conducted within 60 days prior to randomization; randomization must be within 6 months of the transplant date. Patients must have undergone HDT and ASCT within 12 months of the start of induction therapy.
- Maintenance Phase: Comprised of up to thirty-six, 28-day cycles. Patients will be randomized to receive maintenance treatment with SC daratumumab in combination with lenalidomide or lenalidomide alone. Study treatment will continue until confirmed progressive disease (PD), unacceptable toxicity, withdrawal from study or the end of study maintenance phase.
- EOT Visit: An EOT visit is to be scheduled 30 days (\pm 7 days) after the last dose of study treatment(s) or, if a patient begins new therapy for multiple myeloma, as soon as possible prior to the start of next-line therapy.
- Follow-up Phase: After the EOT visit, patients will continue to be followed until the end of the study. The end of the study is defined as 36 months from the date of randomization of the last patient. If a patient has died, the date and cause of death will be collected and documented in the eCRF.

Planned enrollment includes a total of 214 patients to be randomly allocated in a 1:1 ratio to one of the two treatment arms, with randomization stratified by cytogenetic risk at screening as determined by the investigator (high risk versus standard/unknown risk).

Study evaluations will include evaluation of the following:

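### The infection-by-period summary in SAP 6.3.2 counts first infections only and states no denominator, so later periods are understated, more so in the arm with more early infections

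*SAP*

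**What the plan says.** SAP 6.3.2 plans two displays of infections. The main one is "A summary of number of subjects with 1 or more treatment-emergent infections and infestations", by preferred term, for all grades, Grade 3 or 4, Grade 5 and SAEs. The second divides infections by time: "Additional summary analysis will be performed by onset time", with cut points at 6 and 12 months, "based on the first onset of the infections and infestations". The section does not give a denominator for each period. It also does not say whether first onset means the first infection of any kind or the first of each preferred term.

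SAP 6.1 sets the general rule that at each level of summary "a subject is counted once if one or more events were recorded". It defines treatment-emergent events as "any AE that occurs after start of the first study treatment through 30 days after the last study treatment", or up to the day before subsequent antimyeloma therapy if that is earlier. SAP 1.2 describes the Maintenance Phase as "Comprised of up to thirty-six, 28-day cycles".

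No other planned table counts all infections by period. The SAP has no exposure-adjusted event rate. Its other displays by time, for Grade 3 or 4 events and for SAEs, also use first onset: "Treatment-emergent SAEs by SOC, PT and by treatment cycle of first onset".

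**The concern.** Treatment lasts up to 36 cycles, so a table of infections by period will be read as showing whether the risk persists. Counted by first onset, the table cannot show that for infections as a group. A subject infected in month 2 and again in months 9 and 20 appears only in the first row. Each later row draws on a shrinking pool of infection-free subjects, and the pool shrinks faster in the arm with the higher rate. A constant risk then looks as if it fades, and the difference between arms in the later rows is biased in favour of the arm with more early infections.

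The documents suggest which arm that may be. For an earlier daratumumab trial, Protocol 3.2.1 reports Grade 3 or 4 pneumonia in 13.7% with daratumumab and 7.9% without, a ratio of 13.7/7.9 = 1.7.

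The periods also differ in length: two of 6 months and a last one of up to about 21 months, with no time base.

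**Working it through.** The section states no figure to reproduce, so the check asks how far first-onset counts depart from the share of subjects infected in each period.

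**Inputs from the documents.** Maximum treatment is 36 × 28 days = 1,008 days, or 1,008/30.4375 = 33.1 months. The last period is therefore up to 33.1 − 12 = 21.1 months, ignoring the 30 days after the last dose. There are 107 subjects per arm (SAP 1.4).

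**Assumptions.** Each subject has a constant infection rate λ per month, there is no dropout, all treated subjects form the denominator, and first onset means the first infection of any kind. The rates are illustrative, with DR at 1.5 times R.

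**Formulas.**
- First-onset share: up to 6 months 1 − exp(−6λ); 6 to 12 months exp(−6λ) − exp(−12λ); over 12 months exp(−12λ) − exp(−33.1λ).
- Share with any infection starting after month 12: 1 − exp(−21.1λ).
- First-onset share divided by true in-period share: exp(−6λ) for 6 to 12 months and exp(−12λ) for over 12 months. This falls as λ rises, which is why the higher-rate arm is understated more.

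**Results for the period over 12 months.**

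| Rate per month, R / DR | First onset, R / DR | Any onset, R / DR | Order |
|---|---|---|---|
| 0.02 / 0.03 | 27.1% / 32.7% | 34.4% / 46.9% | kept |
| 0.03 / 0.045 | 32.7% / 35.7% | 46.9% / 61.3% | kept |
| 0.04 / 0.06 | 35.3% / 35.0% | 57.0% / 71.8% | about equal |
| 0.05 / 0.075 | 35.8% / 32.3% | 65.2% / 79.5% | reversed |
| 0.08 / 0.12 | 31.2% / 21.8% | 81.5% / 92.1% | reversed |

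Worked example at 0.12: exp(−1.44) − exp(−3.97) = 0.237 − 0.019 = 0.218. In subjects, the 0.08 / 0.12 row is about 33 (R) and 23 (DR) of 107 by first onset, against about 87 and 99 with an infection in the period.

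**Understatement without reversal.** At 0.03 / 0.045 the last-period figures are exp(−0.36) = 70% (R) and exp(−0.54) = 58% (DR) of the true ones. For 6 to 12 months at 0.04 / 0.06 the ratios are exp(−0.24) = 79% and exp(−0.36) = 70%, so the figures are 21% and 30% too low.

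**Where reversal begins.** Setting the two last-period shares equal gives R rates of about 0.043, 0.039 and 0.033 per month for DR/R ratios of 1.25, 1.5 and 2. At those rates 40%, 37% and 33% of R subjects have been infected by month 12.

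**Sensitivity.**
- *Subjects differ in susceptibility.* With gamma frailty of variance 1 at 0.08 / 0.12, first onset gives 23.6% (R) and 20.9% (DR), against 62.8% and 71.7% with any infection. The reversal remains but is smaller.
- *Infection-free denominator.* First onsets over subjects infection-free at month 12 give 81.5% and 92.1% at 0.08 / 0.12 under a constant rate, which is the right order. With frailty of variance 1 they give 46.3% and 50.9%: right order, narrower gap.

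**The case against.** The strongest reply is that the section calls this an additional summary by onset time and states its rule openly. A distribution of time to first infection is a legitimate display and misleads only if read as incidence per period. That is fair. But no companion table gives incidence per period, so this one will be used for that purpose.

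Three stronger readings are tempting, and the documents do not support them.

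- *The higher-rate arm will look better after month 12.* This needs frequent infections and an all-treated denominator. No infection rate for this trial is given, and no denominator is stated. At R rates of 0.03 or below with a ratio of 1.5 the order is kept.
- *Early-infected subjects always drop out of later rows.* If first onset is applied per preferred term, a subject with three different infections can appear in all three periods. Depletion is then small for uncommon terms. The pneumonia figures show a direction from another trial and do not supply an any-grade rate.
- *The Grade 3 or 4 and SAE by-cycle tables share the defect to the same degree.* They use the same rule, but they are laid out by term, where depletion is small for uncommon terms. Their error was not calculated.

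It is also true that an overall excess of infections would still show in the main table, and that the safety analyses are descriptive (Protocol Synopsis, Safety Analyses).

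**Conclusion.** The point holds for the additional by-period summary in SAP 6.3.2, with infections taken as a group. Over all treated subjects, later periods are understated at any positive infection rate, and more in the arm with more early infections. At assumed rates of 0.03 and 0.045 per month, the last-period figures are 70% and 58% of the true ones.

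Reversal after month 12 is a possibility, not a prediction. It requires all treated subjects as the denominator and roughly a third or more of R subjects infected by month 12, which is an R rate of about 0.04 per month or more (0.033 to 0.043, depending on the rate ratio). Overall incidence by preferred term, grade and seriousness is untouched, and no efficacy result or error rate is involved. The change is worth making because the stated rule biases the one planned display of infection over time.

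**What to change.** In SAP 6.3.2, define the by-period summary as follows.

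- **Numerator:** subjects with any treatment-emergent infection starting in the period, for infections as a group and by preferred term.
- **Denominator:** subjects still in the treatment-emergent window at the start of the period, with the number shown.
- **Time base:** infection events per 100 patient-months observed in the period, because the last period is up to about 21 months long against 6 for the others.
- **First onset:** if kept, a separately labelled column that states whether it applies to any infection or to each preferred term.

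Adverse event onset dates and dosing dates are already collected, so no new data are needed. The cost is SAP wording and minor reprogramming of a descriptive table. Extending the same counting to the Grade 3 or 4 and SAE by-cycle tables in SAP 6.1 is optional.

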6.3.3. Opportunistic Infection

Opportunistic infection events refer to the adverse events defined by SMQ search of "opportunistic infections (SMQ)". These TEAEs will be summarized by SOC and PT for all grades, Grade 3 or 4, Grade 5, and SAEs.

6.3.4. COVID-19 Infections

To evaluate COVID-19 pandemic's impact on the study, TEAEs of COVID-19 infections will be summarized by MedDRA SOC and PTs for all grades, Grade 3 or 4, Grade 5, and SAEs. The COVID-19 TEAEs will be identified through PTs which contain text string of "COVID-19".

All COVID19 TEAEs will be listed with subjects vaccination status displayed for COVID-19.

6.3.5. Hemorrhage Events

Hemorrhage events refer to the adverse events defined by Standardized MedDRA Queries (SMQ) with the first subcategory SMQ of hemorrhage terms (exclude laboratory terms). Incidences will be summarized by MedDRA SOC and PT for all grades, Grade 3 or 4, Grade 5, and SAEs.

6.3.6. Cytopenia

Cytopenia will be identified by the following PTs and grouped into 4 categories. They will be summarized by MedDRA SOC and PT for all grades, Grade 3 or 4, Grade 5, and SAEs:

- Neutropenia
 - Agranulocytosis

- Granulocyte count decreased
- Granulocytopenia
- Neutropenic infection
- Neutrophil count abnormal
- Neutrophil count decreased
- Neutropenia
- Febrile neutropenia
- Anaemia
 - Anaemia
 - Anaemia macrocytic
 - Anaemia megaloblastic
 - Autoimmune haemolytic anaemia
- Thrombocytopenia
 - Megakaryocytes decreased
 - Platelet count decreased
 - Platelet production decreased
 - Thrombocytopenia
 - Thrombotic thrombocytopenic purpura
 - Acquired amegakaryocytic thrombocytopenia
 - Amegakaryocytic thrombocytopenia
 - Congenital thrombocytopenia
 - Heparin-induced thrombocytopenia
 - Immune thrombocytopenic purpura
 - Non-immune heparin associated thrombocytopenia
 - Neonatal alloimmune thrombocytopenia
 - Severe fever with thrombocytopenia syndrome
 - Spontaneous heparin-induced thrombocytopenia syndrome
 - Thrombocytopenic purpura
- Lymphopenia
 - Lymphocyte count decreased

- B-lymphocyte count decreased
- T-lymphocyte count decreased
- Lymphopenia

6.3.7. Hepatitis B virus reactivation

Hepatitis B virus reactions TEAEs will be summarized by SOC and PT for all grades, Grade 3 or 4, Grade 5, and SAEs. Hepatitis B virus reactions can be identified by PT as below:

- Hepatitis viral
- Acute Hepatitis B
- Hepatitis B
- Hepatitis B reactivation
- Chronic Hepatitis B
- Hepatitis B DNA assay positive
- Hepatitis B DNA increased

6.3.8. Other Malignancy

Other malignancies will be grouped and summarized by treatment groups. A listing of subjects who reported other malignancies during the study will be provided. This listing will include diagnosis, study day of diagnosis, recurrence of a prior existing malignancy (yes, no), pathology diagnosis (biopsy, aspirate, etc.), outcome, treatment for malignancies and other information whenever a new malignancy is observed.

6.4. Adverse Events by Subgroups

The following subgroup analysis of AEs will be performed based on subgroups specified in Section 2.4:

- Overview of TEAEs
- All TEAEs

6.5. Clinical Laboratory Tests

On-site or accredited local laboratory must be used for hematology laboratory assessments. Results of local hematology tests must be evaluated before each study treatment administration to guide treatment decisions.

Applicable laboratory results will be graded according to NCI-CTCAE version 5.0. The worst toxicity grade in hematology and chemistry during the treatment will be summarized by treatment group and toxicity grade. Shift tables from baseline to worst toxicity grade during the treatment will be provided for each laboratory analyte listed below. These tables will summarize the number of subjects with each baseline CTC grade and changes to the maximum CTC grade.

Hematology parameters include:

- hemoglobin
- neutrophils
- lymphocytes

Chemistry parameters include:

- sodium
- potassium
- creatinine
- corrected calcium
- bilirubin

- platelet
- white blood cell (WBC)
- alkaline phosphatase
- albumin
- glucose
- aspartate aminotransferase (AST)
- alanine aminotransferase (ALT)

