Hematology and serum chemistry*	x	 Hematology: Lenalidomide only arm: D1 of every cycle, ie, C1D1, C2D1, C3D1, C4D1, C5D1, C6D1, C7D1, C8D1, C9D1, C10D1, C11D1, C12D1, etc, up to C36D1. Lenalidomide + Daratumumab Arm: D1, D8, D15, D22 of Cycles 1 and 2; D1, D15 of Cycles 3, 4, 5, and 6; D1 of every cycle from C7 onwards (ie, C7D1, C8D1, C9D1, C10D1, C11D1, C12D1, C13D1, C14D1, C15D1, C16D1, etc.) Serum chemistry: Lenalidomide only arm: D1 of Cycles 1 through 6 (ie, C1D1, C2D1, C3D1, 	x	-	 On-site or accredited local laboratory must be used for hematology laboratory assessments. Results of local hematology tests must be evaluated before each study treatment administration to guide treatment decisions. Hematology panel to include: Hgb, WBCs with absolute neutrophils and lymphocytes, RBCs, and platelet count. Serum chemistry panel to include: Sodium, potassium, serum creatinine and creatinine clearance (CrCl) (must be calculated as described in Section 9.2.2), glucose, AST, ALT, total bilinubin, alkaline phosphatase, BUN, calcium and albuminadjusted calcium (see Section 9.2.3), and albumin. Note that albumin and serum calcium corrected for albumin will also be obtained on C1D1 from the central laboratory as described below under Disease evaluations, laboratory evaluations.

		STUDY PHA	SES/VISI	rs ^a	
Procedure	SCREENING	Maintenance (Cycles 1 – 36)	ЕОТ	Follow-up (from the date of last study treatment until the end of study)	Notes
		C4D1, C5D1, C6D1), and every 3^{rd} cycle thereafter (ie, C9D1, C12D1, C15D1 C18D1, C21D1, C24D1, C27D1, C30D1, C33D1 and C36D1) Lenalidomide + Daratumumab arm: D1, D8, D15, D22 of Cycles 1- 2; D1, D15 of Cycles 3-6; D1 of every 3^{rd} cycle thereafter (ie, C9D1, C12D1, C15D1, C18D1, C21D1, C24D1, C27D1, C30D1, C33D1 and C36D1)			
		On C1D1 and D1 of subsequent cycles, there is no need to repeat the tests if performed within the past 3 days. In addition, tests may be repeated as clinically indicated. Results must be evaluated before each daratumumab administration or beginning of new cycle of lenalidomide administration.			

		STUDY PHA	SES/VISI	TS ^a	
Procedure	SCREENING	Maintenance (Cycles 1 – 36)	ЕОТ	FOLLOW-UP (FROM THE DATE OF LAST STUDY TREATMENT UNTIL THE END OF STUDY)	NOTES

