11.5. Benefit-risk Analyses

For benefit risk analyses, between-treatment differences will be shown with absolute rate or other difference measures and corresponding 95% CIs. Both continuous and dichotomized versions of continuous endpoints will be shown. Results will be displayed in tabular and forest plot form. Additional details will be provided in the separate benefit-risk SAP.

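### Worst-grade laboratory tables by arm (SAP 6.5) are biased upward in the daratumumab arm, which has ten more scheduled draws in Cycles 1-6

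*SAP*

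**What the plan says.** SAP 6.5 (Clinical Laboratory Tests) states: "The worst toxicity grade in hematology and chemistry during the treatment will be summarized by treatment group". It adds: "Shift tables from baseline to worst toxicity grade during the treatment will be provided for each laboratory analyte listed below". Neither output is limited to visits that both arms share, and the section does not mention that the arms are sampled on different schedules.

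The schedules are in the protocol, Time and Event Schedule - Part 1, row for hematology and serum chemistry:

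- Hematology, combination arm: "D1, D8, D15, D22 of Cycles 1 and 2; D1, D15 of Cycles 3, 4, 5, and 6", then "D1 of every cycle from C7 onwards".
- Hematology, control arm: "Lenalidomide only arm: D1 of every cycle, ie, C1D1, C2D1, C3D1, C4D1, C5D1, C6D1", continuing to Cycle 36.
- Chemistry, combination arm: "D1, D8, D15, D22 of Cycles 1- 2; D1, D15 of Cycles 3-6", then every third cycle.
- Chemistry, control arm: "Lenalidomide only arm: D1 of Cycles 1 through 6", then every third cycle.

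SAP 6.6 does acknowledge an unequal schedule, but for vital signs, which are summarized by scheduled time point and not by worst value.

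**The concern.** The worst grade is a maximum over the samples taken. In Cycles 1-6 the combination arm's scheduled days include every control-arm day plus ten more. For any given course of blood values, the worst grade seen on the fuller schedule cannot be lower than the one seen on Day 1 alone, and it will often be higher. The two columns of the table therefore differ in expectation even if the drugs are equally toxic, and the direction is known: against the daratumumab arm.

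A reader of the by-arm tables could not separate a drug effect on neutrophils, platelets or transaminases from the effect of more frequent sampling.

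**Working it through.** **Counts (from the schedule).**

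- Cycles 1-6, combination arm, both panels: 4 × 2 + 2 × 4 = 16. This agrees with the 8 + 8 daratumumab doses in protocol Table 2.
- Cycles 1-6, control arm, both panels: 1 × 6 = 6.
- Cycles 7-36: hematology 30 in each arm; chemistry 10 in each arm (Cycles 9, 12, ..., 36).
- All 36 cycles: hematology 16 + 30 = 46 vs 6 + 30 = 36; chemistry 16 + 10 = 26 vs 6 + 10 = 16.
- SAP 2.6 makes the last value on or before first dosing the baseline. A pre-dose Cycle 1 Day 1 draw is therefore not post-baseline, which leaves 15 vs 5 in Cycles 1-6, and 45 vs 35 (hematology) and 25 vs 15 (chemistry) overall.

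The documents give no sample totals or per-draw abnormality rates, so there is no planned figure to reproduce. Everything below is illustration on assumed inputs.

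**Independent draws, as an upper illustration.** With the same probability p of an abnormal draw in both arms, the chance of at least one in k draws is 1 − (1 − p)^k.

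- p = 3%, Cycles 1-6: 1 − 0.97^15 = 36.7% vs 1 − 0.97^5 = 14.1%.
- p = 5%, Cycles 1-6: 1 − 0.95^15 = 53.7% vs 1 − 0.95^5 = 22.6%.
- p = 5%, 36 cycles, hematology: 1 − 0.95^45 = 90.1% vs 1 − 0.95^35 = 83.4%.

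Blood counts within a patient are not independent, so these should not be the headline.

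**Correlated draws.** I simulated one latent normal process for both arms (100,000 patients) on the scheduled days. It has a between-patient variance share of 0.3 or 0.6 and a within-patient correlation of 0.5 or 0.8 per week, decaying with the days between draws. A draw is abnormal above the 1 − p quantile. The ranges span the four combinations, with Cycle 1 Day 1 excluded.

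| Period | Panel | Draws | Excess, p = 3% | Excess, p = 5% |
|---|---|---|---|---|
| Cycles 1-6 | both | 15 vs 5 | 4.4 to 12.2 points | 5.9 to 16.0 points |
| Through Cycle 12 | hematology | 21 vs 11 | 2.9 to 9.0 | 3.8 to 10.9 |
| Through Cycle 12 | chemistry | 17 vs 7 | 3.7 to 10.9 | 4.8 to 13.9 |
| All 36 cycles | hematology | 45 vs 35 | 1.4 to 4.2 | 1.6 to 4.3 |
| All 36 cycles | chemistry | 25 vs 15 | 2.4 to 7.6 | 2.9 to 8.9 |

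At p = 5% the Cycles 1-6 rates behind these differences are roughly 19-35% vs 13-19%.

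The middle rows matter because the primary analysis (protocol 11.6) takes place once all patients have completed 12 months or stopped. The last patients randomized then have about 365 / 28 ≈ 13 cycles. Chemistry dilutes more slowly than hematology because it is drawn only every third cycle after Cycle 6. Patients who stop within Cycles 1-6 hardly dilute at all.

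**The case against.** The strongest reply is about size and consequence.

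- **Dilution.** The tables run over the whole treatment period, so 16 to 6 is not the ratio behind them for a patient who completes 36 cycles. This stands. It reduces the hematology artifact to a few points, but it does not remove it, and it helps least for chemistry and for early stoppers.
- **No test.** A reader might infer a formal comparison or a type I error problem. The documents do not support that: the protocol's statistical synopsis plans no inferential analysis of safety data. The harm is to a descriptive contrast.
- **Benefit-risk.** A reader might infer that the bias enters the benefit-risk analysis, where "between-treatment differences will be shown with absolute rate or other difference measures and corresponding 95% CIs" (protocol 11.5). Protocol 9.6 speaks only of key safety endpoints, and the details are left to a separate plan. Carry-over is possible but not documented.
- **A time-aligned view exists.** Protocol 11.4 promises laboratory values and changes at each scheduled time point, and SAP 2.1 uses nominal cycles in general. That helps for means, but it does not give worst grades on common visits. The rules for choosing one record per visit date or window (SAP 2.1 and 2.7) do not clearly cure it either, since Days 8, 15 and 22 are separate scheduled draws.
- **A Day 1 table has its own bias.** Protocol Table 3 makes the start of each cycle conditional on neutrophils, platelets and hemoglobin. Day 1 draws at the actual cycle start are therefore selected for recovered counts, and nadirs between cycles are lost. This stands, and it limits the remedy.
- **Unscheduled draws** are allowed in both arms in unknown number, and could narrow or widen the gap.

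**Conclusion.** The point holds as a directional bias in descriptive safety tables. With equal toxicity and scheduled draws only, the worst-grade and shift tables will show more abnormality in the daratumumab arm. On the assumed inputs (3-5% per draw, between-patient share 0.3-0.6, weekly correlation 0.5-0.8), the excess is about 4 to 16 points over Cycles 1-6. Through Cycle 12 it is about 3 to 11 points for hematology and 4 to 14 for chemistry. Over 36 cycles it is about 1 to 4 and 2 to 9 points respectively. The direction follows from the schedule; the size rests on inputs that the documents do not supply.

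Two stronger readings should be resisted. The Cycles 1-6 gap is not the gap in the planned tables for patients who complete treatment, because sampling is equal from Cycle 7. Nor does the problem justify replacing the all-draws tables with Day 1 tables, for the reason that Table 3 supplies. The primary endpoint is untouched.

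**What to change.** In SAP 6.5:

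1. Keep the all-draws worst-grade and baseline-to-worst shift tables as planned, and footnote the unequal schedule in Cycles 1-6.
2. Add supplementary versions of both, restricted to the Day 1 draws scheduled in both arms. Count the first Day 1 draw of each cycle even if it led to a cycle hold. This gives 6 vs 6 scheduled draws in Cycles 1-6 (5 vs 5 post-baseline). Over 36 cycles it gives 36 vs 36 for hematology and 16 vs 16 for chemistry.
3. Report the number of post-baseline draws per patient by arm, including unscheduled ones.
4. State that the two sets are read together and that the Day 1 version is not by itself the between-arm comparison.

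The cost is one extra set of tables from data already collected, with no change to monitoring. The Day 1 version misses mid-cycle nadirs and remains affected by the re-treatment thresholds, which its footnote should say.
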